Children requiring prolonged courses of PN are at risk for developing PN associated liver disease. We hypothesize that although omega-6 fatty acid emulsions prevent fatty acid deficiency, they are not cleared in a manner similar to enteral chylomicrons and therefore accumulate in the liver and resulting in steatotic liver injury. We further hypothesize that a fat emulsion comprised of omega-3 fatty acids (i.e., fish oil) such as Omegaven® would be beneficial in the management of steatotic liver injury by its inhibition of de novo lipogenesis, the reduction of arachidonic acid-derived inflammatory mediators, prevention of essential fatty acid deficiency through the presence of small amounts of arachidonic acid, and improved clearance of lipids from the serum. Animal studies have shown that IV fat emulsions (IFE) such as fish oil that are high in eicosapentaenoic and docosahexaenoic acid reduce impairment of bile flow which is seen in cholestasis caused by conventional fat emulsions. Furthermore, we hypothesize that that intravenous omega three fatty acids will be well tolerated and might reduce the inflammatory effect in the liver of prolonged PN exposure and could potentially reverse any hepatic dysfunction due to PN/IFE use. By administering Omegaven® in place of conventional phytosterol/soybean fat emulsions we may reverse or prevent the progression of PN associated cholestasis and thus allow the patient to be maintained on adequate PN until they are able to ingest adequate nutrition enterally.

1. Specific Aims /Objectives

1. To determine the safety profile of an intravenous omega-3 fat emulsion (Omegaven®)

Hypothesis for Aim 1:

1.1 – After starting Omegaven® on PN, the rate of fatty acid deficiencies and imbalances will be as low as before Omegaven®. Also, the rate of triglyceride events > 400 mg/dL with Omegaven® will be similar to that seen with PN administered with soy oil IFE (conventional emulsion, i.e., Intralipid®).

1.2 – PN containing Omegaven® will be safe for patients with respect to the risk of unexpected bleeding, coagulopathies, and other adverse events.

1.3 – PN containing Omegaven® will promote more short-term growth and development than conventional fat emulsions.

2. To determine if established PN associated liver disease can be reversed or its progression halted by using a parenteral fat emulsion prepared from fish oil as measured by normalization of serum levels of hepatic enzymes and bilirubin.

Hypothesis for Aim 2:

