The number of subjects included in the Omegaven® group will be based on a compassionate use protocol and not on study power considerations. The number of subjects included in the soybean oil fat emulsion historical cohort group will not be based on study power considerations but rather on the number of eligible subjects from a pre-existing cohort.

The primary safety analysis will be descriptive and not based on statistical significance. However, in Table 4 we outline power to detect several differences in the frequency of adverse events, assuming 20, 25, or 30 patients, diverse proportion of subjects with adverse event in either treatment period and not with the adverse event in the other (proportion of discordant pairs), for a two-sided 5% significance level McNemar's tests. Table 5 includes estimates of power for a Fisher's exact test when comparing Omegaven® with historical control groups, assuming diverse frequency of occurrence of the adverse event in the control group, equal number of subjects in each group, and diverse differences in proportions between Omegaven® and soybean oil fat emulsion groups.

For lower proportions of discordant pairs, we would generally attain close to 80% power in McNemar's test. Even for higher proportions of discordant pairs, assuming the high differences between before and after treatment that we expect to observe, e.g., 50% or more, 80% power can be attained in McNemar's test (Table 4). In Fisher's exact test, we will attain 80% power or more to detect differences between Omegaven® and historical controls of 45% or larger, regardless of the frequency of adverse events in each group (Table 5).

Table 4 – Power to detect varying differences in proportions before and after treatment with Omegaven® in a McNemar's test. All calculations were based on an alpha significance level of 0.05.

Difference between proportions	Proportion of discordant pairs	McNemar's Test		
		Sample size in the Omegaven™ group		
		20	25	30
30%	40%	59%	72%	81%
	60%	44%	55%	63%
50%	60%	92%	97%	99%
	80%	79%	88%	93%
80%	85%	>99%	>99%	>99%
	95%	>99%	>99%	>99%

*Calculations performed Statxact.

Table 5 – Power to detect varying differences in proportions between Omegaven® and historical control groups in a Fisher's exact test. All calculations were based on an alpha significance level of 0.05.

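### Safety hypotheses of no worsening and similarity are backed only by difference tests and by power for 45- to 50-point differences; estimates with confidence intervals are needed, and the power text needs correcting

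*Combined protocol and SAP*

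**What the plan says.** Section 1 (Specific Aims), Hypothesis 1.1, makes two safety predictions. Within Omegaven patients, "the rate of fatty acid deficiencies and imbalances will be as low as before". Against the soybean group, the rate of triglyceride values above 400 mg/dL "will be similar to that seen with PN administered with soy oil IFE". Neither comes with a margin.

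Section 5c (Analysis of Safety and Tolerability) bases all primary safety analyses on descriptive statistics. It adds significance assessments as secondary analyses: paired tests before versus after, and Fisher's exact, Wilcoxon or t-tests between groups, the latter for exploratory purposes.

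Section 5d says that neither group's size rests on power and that the primary safety analysis does not rest on significance. It then tabulates power "assuming 20, 25, or 30 patients". Table 4 covers before/after differences of 30, 50 and 80 points and is described as "for a two-sided 5% significance level McNemar's tests". Table 5 covers Fisher's exact test for differences of 35 and 45 points, with "equal number of subjects in each group". The text concludes that 80% power can be reached before/after by "assuming the high differences between before and after treatment that we expect to observe, e.g., 50% or more". Against historical controls it claims at least 80% power for 45 points or more, whatever the event frequency.

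**The concern.** A hypothesis of no worsening or similarity is supported by showing that a material excess is unlikely. Power to detect a very large difference does not show that. The two hypotheses are therefore left without a matching analysis: the planned inference is a set of difference tests, and the only quantified capability concerns differences far larger than a safety review would want to rule out.

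The phrase about expected differences also fits Hypothesis 1.1 badly. If it means an increase in events, it conflicts with the prediction. If it means a decrease, it does not describe the ability to detect harm. The text does not say which.

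What is at stake is how the results are reported. With 20 to 30 patients, a non-significant comparison is likely even if the event rate rises materially, and a reader of the final report could take it as evidence for Hypothesis 1.1.

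**Working it through.** **Inputs.** From section 5d: n = 20, 25 or 30, equal groups for Fisher's test, two-sided alpha 0.05, and the differences and discordant proportions in Tables 4 and 5. The documents give no expected event rates and no margins, so the smaller rises used in steps 4 and 5 are assumptions.

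**1. Table 4 (McNemar).** Let δ be the difference and ψ the discordant proportion. The discordant count is D ~ Bin(n, ψ). Given D, the count in one direction is B ~ Bin(D, (ψ+δ)/(2ψ)). The exact test compares B with Bin(D, ½). For δ = 0.50 and ψ = 0.80, (0.80+0.50)/1.60 = 0.8125. Power in %, at n = 20/25/30:

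| δ, ψ | Printed | Two-sided 5% exact | One-sided 5% exact |
|---|---|---|---|
| 30, 40 | 59/72/81 | 46/60/71 | 58.5/71.6/81.4 |
| 30, 60 | 44/55/63 | 31/41/50 | 43.7/54.6/63.4 |
| 50, 60 | 92/97/99 | 86/94/98 | 91.9/97.2/99.0 |
| 50, 80 | 79/88/93 | 68/79/87 | 79.3/88.0/93.0 |

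All 12 printed cells match the one-sided test. A two-sided asymptotic test misses by more than 2 points in 5 of them. The 80-point rows are 99% or more either way. At 50 points with 80% discordance, two-sided power reaches 80% only at n = 30.

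**2. Table 5 (Fisher).** Full enumeration of the two-sided test reproduces all 18 cells. One of them, 45 points from a 25% frequency at n = 20, is printed as 73% (recomputed 73.1%). That contradicts the sentence claiming at least 80% at any frequency.

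**3. Largest non-significant harm, paired.** Suppose no patient has the event before treatment.
- Five new events: p = 2 × 0.5^5 = 0.0625, not significant.
- Six new events: p = 2 × 0.5^6 = 0.031, significant.
- Five new events are an observed rise of 5/20 = 25, 5/25 = 20 and 5/30 = 17 points.
- The exact (Clopper-Pearson) upper 95% limit on the proportion with a new event, the 0.975 quantile of Beta(6, n−5), is 49, 41 and 35%.

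**4. Paired power for a moderate rise (assumed).**
- 15-point rise, 20% discordant (17.5% worse, 2.5% better): 8.5, 17 and 26.5% at n = 20/25/30.
- 20-point rise with every discordant pair harmful: 20, 38 and 57%.

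**5. Between groups.**
- Non-significant example at n = 20 per group: 6 versus 1 events, Fisher p = 0.091, difference 25 points, Newcombe 95% interval about 1 to 47.
- Non-significant example at n = 30 per group: 7 versus 1 events, p = 0.052, difference 20 points, interval about 2 to 38.
- Power at assumed rates of 5% versus 20%: 17, 20 and 24% at n = 20/25/30. At 5% versus 30%: 45, 55 and 63%.

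**The case against.** Four stronger readings are tempting, and the documents do not support them.

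- *That safety will be concluded from failure to reject.* Sections 5c and 5d make the primary safety analysis descriptive and the tests secondary or exploratory. No passage ties Aim 1 to a p-value. The misreading is a foreseeable risk, not a planned rule.
- *That the power tables justify the sample size.* Section 5d says enrolment follows compassionate use and the control number follows the existing cohort. The values 20, 25 and 30 are illustrations, and N is not capped at 30.
- *That both hypotheses lean on 50 points.* That figure belongs to the before/after test only. The triglyceride comparison is between groups, where the text relies on 45 points. The tables also show 30 and 35.
- *That the plan flatly contradicts itself by expecting 50-point harm.* The phrase names no endpoint or direction, and section 5c anticipates improvement in some measures, such as INR and pre-albumin. It is ambiguous and needs reconciling, but a contradiction is not shown.

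It is also fair to say that a small sample does not leave every result uninformative. Zero events in 20, 25 or 30 patients gives an upper limit of 1 − 0.025^(1/n) = 16.8, 13.7 or 11.6% (two-sided 95%), although this bounds an absolute rate and not a difference between periods or groups.

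These points lower the severity. They do not supply an analysis suited to Hypothesis 1.1: descriptive summaries without a stated measure of precision, plus difference tests, leave the similarity question unanswered.

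**Conclusion.** The point holds as a reporting and wording weakness that should be corrected, not as a flawed decision rule. The plan states no-worsening and similarity hypotheses, gives no margin or interval rule, and describes its capability only through power for large differences. Non-significance at the tabulated sizes is compatible with upper limits of 35 to 49% for new events in the paired case, and 38 to 47 points in the between-group examples.

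The paired limits take the before-treatment count as zero. The power figures of 8.5 to 26.5% rest on an assumed 15-point rise with 20% discordance, and other assumptions give other values, as the working shows. The findings on Table 4 and on the Table 5 sentence need no assumption beyond the section's own inputs and an exact McNemar test.

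**What to change.** 1. Delete the phrase about expected before/after differences, or give its endpoint and direction and reconcile it with Hypothesis 1.1.
2. Make the primary descriptive safety statement, for each endpoint, the paired or between-group difference with its 95% confidence interval.
3. State that a non-significant p-value will not be read as similarity or as no worsening.
4. State the excess that the achieved N can exclude, and label any assumed event or discordance rates as assumptions.
5. Restate Table 4 as two-sided (68/79/87% at 50 points with 80% discordance, and likewise for the other rows), or relabel it as one-sided and amend the text.
6. Correct the sentence claiming at least 80% power at any event frequency so that it agrees with the 73% cell in Table 5.

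The cost is SAP and protocol wording. No new patients or data are needed. The downside is that the stated safety capability becomes less favourable.

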Differences in the frequency of the event between Omegaven® and historical control groups	Frequency of the event in one of the comparison groups	Fisher's Exact Test		
		20	25	30
35%	5%	72%	82%	89%
	25%	49%	65%	72%
	50%	57%	68%	78%
45%	5%	89%	95%	98%
	25%	73%	88%	92%
	50%	89%	95%	98%

*Calculations performed using N-query advisor.

e. Study Organization

[name] will serve as the principal investigator. [name] will serve as the managing co-investigator. [name], [name], [name], [name], and [name] will assist with patient enrollment. Drs. [name], [name], and [name] along with the CRP staff will assist in study design and data analysis. Data collection will be done by the research nurses, with assistance from the nursing unit liaisons, the study coordinator, and research assistants in [name] lab. All individuals who assist in this function will have CITI training. The necessary CCI amendments and approvals will be obtained prior to any staff assisting in this function. The study coordinator will abstract the medical records and complete the CRFs and a careful QC visual inspection of the CRFs prior to submitting them for data entry. The Research Coordinator will complete all data entry..

f. Data and Safety Monitoring Plan

Patients will be monitored while receiving Omegaven® treatment to observe for signs of Omegaven® toxicity. At the start of Omegaven® therapy, patients will be monitored closely during and shortly after initial Omegaven® administration to observe for signs of allergic reaction and anaphylaxis. In the event the patient demonstrated signs or symptoms of allergic reaction, the Omegaven® will be discontinued and the PI and attending physician will be notified. Selected safety labs will be evaluated by attending staff

and the Study Investigators for both clinical and research purposes. Blood samples will be taken prior to the start of therapy (baseline), and thereafter in accordance with the scheduled represented in the tables below.

Reversal/Safety Study Lab Schedule:

Patient Status	Parameter	Tests to be Performed	Frequency
Inpatient/receiving Omegaven®	Direct bilirubin >2 mg/dL	PN profile, AST, GGT, CRP, lipid Panel, PT, PTT, INR, fibrinogen, EFA Panel	Weekly
	Direct bilirubin ≤2 mg/dL	PN profile	Weekly
		PN profile, AST, GGT, CRP, PT, PTT, INR, fibrinogen, EFA panel, lipid panel	Monthly
Inpatient/off Omegaven®			
		PN profile, AST, GGT, CRP, lipid Panel, PT, PTT, INR, fibrinogen, EFA Panel	one complete set of post-Omegaven labs

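### The sentence claiming at least 80% power for any 45-point difference contradicts Table 5, which gives 73% for 25% versus 70% at 20 per group

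*Combined protocol and SAP*

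**What the plan says.** Section 5d describes the between-group calculation as follows: "Table 5 includes estimates of power for a Fisher's exact test when comparing Omegaven® with historical control groups". The groups are assumed equal ("equal number of subjects in each group"), the tabulated sizes are 20, 25 and 30, and the note to the table reads "All calculations were based on an alpha significance level of 0.05". The rows are indexed by "Frequency of the event in one of the comparison groups", at 5%, 25% and 50%, for differences of 35 and 45 points.

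The text then summarises the table: "we will attain 80% power or more to detect differences between Omegaven® and historical controls of 45% or larger, regardless of the frequency". No group size is attached to that statement.

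The 45-point block of Table 5 gives, for 20 / 25 / 30 per group:

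- frequency 5%: 89% / 95% / 98%
- frequency 25%: 73% / 88% / 92%
- frequency 50%: 89% / 95% / 98%

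The same section says that the size of the Omegaven group "will be based on a compassionate use protocol and not on study power considerations", that the number of controls depends on who is eligible in an existing cohort, and that the primary safety analysis is descriptive.

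**The concern.** The sentence makes a universal claim: whatever the event frequency, a difference of 45 points or more is detected with at least 80% power. One cell of the table it cites is 73%, so the sentence and the table cannot both be right. Either the cell is misprinted or the summary overreaches.

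The sentence is the plan's only verbal summary of what its between-group comparisons of proportions can detect. The analysis plan uses Fisher's test for between-group safety outcomes such as triglycerides ever above 400 mg/dL, and for transplant, death and transfusion. A reader who relies on the sentence would put the chance of missing a 45-point difference at no more than 20%, and would be too reassured by a null comparison in small groups.

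**Working it through.** **Inputs, all from section 5d.** Fisher's exact test; alpha 0.05; equal groups of n = 20, 25 or 30; frequency p1 of 5%, 25% or 50%; p2 = p1 + 0.35 or p1 + 0.45. Sidedness is stated only for the paired test ("for a two-sided 5% significance level McNemar's tests"). Two-sided is assumed here for Fisher's test and checked in step 1.

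**Formula.** Power = Σx Σy Bin(x; n, p1) · Bin(y; n, p2) · 1{two-sided Fisher p-value for (x, y) ≤ 0.05}, summed over all x, y = 0, …, n.

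**Step 1: reproduce Table 5 (printed → recomputed, %).**

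| Difference | Frequency | n = 20 | n = 25 | n = 30 |
|---|---|---|---|---|
| 35 | 5% | 72 → 71.6 | 82 → 82.2 | 89 → 89.3 |
| 35 | 25% | 49 → 49.3 | 65 → 65.4 | 72 → 71.9 |
| 35 | 50% | 57 → 57.3 | 68 → 67.6 | 78 → 77.7 |
| 45 | 5% | 89 → 89.4 | 95 → 95.2 | 98 → 98.2 |
| 45 | 25% | **73 → 73.1** | 88 → 88.1 | 92 → 92.4 |
| 45 | 50% | 89 → 89.4 | 95 → 95.2 | 98 → 98.2 |

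All 18 cells agree to the printed percent, which confirms the two-sided test. For the disputed cell, one-sided Fisher would give 82.3% and an uncorrected chi-square 84.1%, but neither method reproduces the table. The 73% is not a misprint. It also has only one reading: a 45-point difference from 25% must be 25% versus 70%, because 25% − 45% is negative.

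**Step 2: vary the frequency, 45-point difference, n = 20 per group.**

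| Lower frequency | 5% | 10% | 15% | 20% | 25% | 30% | 35% | 40% | 45% | 50% |
|---|---|---|---|---|---|---|---|---|---|---|
| Power (%) | 89.4 | 83.9 | 79.7 | 75.7 | 73.1 | 73.1 | 75.7 | 79.7 | 83.9 | 89.4 |

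Power is below 80% from about 15% to 40%. The minimum is 72.7%, at 27.5% versus 72.5%, so the largest chance of a miss is 100 − 72.7 = 27.3%. On a half-point grid, power is below 75% only for lower frequencies of about 21% to 34%.

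The 5% and 50% rows of the 45-point block are mirror images (5% versus 50%; 50% versus 95%). The block therefore covers only two distinct scenarios, and at n = 20 one of the two falls short.

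**Step 3: minimum power over all frequencies, 45-point difference, equal groups.**

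| n per group | 20 | 21 | 22 | 23 | 24 | 25 | 26 | 27 | 28 | 29 | 30 |
|---|---|---|---|---|---|---|---|---|---|---|---|
| Minimum (%) | 72.7 | 75.6 | 79.4 | 82.8 | 85.7 | 88.1 | 86.4 | 87.1 | 89.1 | 90.7 | 92.3 |

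The claim fails at 20 to 22 per group and holds from 23. The minimum does not rise steadily, because the test is discrete: it dips to 86.4% at 26.

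**Step 4: difference needed at n = 20 per group.** The minimum over frequencies is 79.5% at 48 points and 81.5% at 49 points. About 49 points are needed for 80% power at every frequency.

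**The case against.** The strongest reply is that little depends on the sentence. The primary safety analysis is descriptive, significance between groups is assessed only for exploration, and the primary efficacy comparison uses log-rank and Cox methods that this table does not cover. The 73% is printed in the cited table, and eight of the nine 45-point cells support the sentence.

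The shortfall also depends on both groups having about 20 to 22 patients. Equal size is an assumption of Table 5, not a feature of the design. The section on contemporary historical controls specifies 50 control patients. With 20 treated patients, minimum power for a 45-point difference is about 84% against 25 controls, 88.7% against 30 and 91.9% against 50. The available text gives no number for the older control cohort with direct bilirubin above 2 mg/dL.

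All of this stands as a limit on the consequence. It does not make the sentence true. The sentence cites a table built on equal groups and carries no size restriction, and since power does not set the group sizes, nothing guarantees that small equal groups will not occur.

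A reader might infer that the trial falls short of its intended power at a planned sample size. The documents do not support that: 20, 25 and 30 are sizes assumed for the power tables ("assuming 20, 25, or 30 patients"), not targets.

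**Conclusion.** The point holds as an internal contradiction with a small practical effect. The summary sentence is wrong for 20 per group and right for 25 and 30. At 20 per group, power for a 45-point difference ranges down to 72.7% and is below 80% for lower frequencies of about 15% to 40%. This rests on the two-sided Fisher test at 0.05 with equal groups, the set-up that reproduces the whole table.

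It would go too far to say that a 45-point difference would be missed more than one time in four. That is so only for 20 versus 20 with a lower frequency of about 21% to 34%; outside that band the chance of a miss is smaller. No sample size, decision rule or primary conclusion depends on the sentence.

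**What to change.** Replace the sentence in section 5d with, for example:

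> Assuming equal groups, power for a 45-point difference is at least 88% at any event frequency with 25 or 30 per group. With 20 per group it can be as low as 73%, and a difference of about 49 points is needed for 80% power at any frequency.

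The 88% should be tied to the tabulated sizes of 25 and 30, not to every size from 25 upward, because the minimum is 86.4% at 26 and 87.1% at 27. It would also help to state in the note to Table 5 that the test is two-sided and that the column heads are numbers per group.

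The cost is one sentence and a table note. The stated power becomes slightly less favourable; no analysis, sample size or data collection changes.

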Glucose	X		X	X		
BUN	X		X	X		
Creatinine	X		X	X		
Triglycerides	X		X	X		
Calcium	X		X	X		
Magnesium	X		X	X		
Phosphorus	X		X	X		
Prealbumin	X		X	X		
C reactive protein	X		X	X		
Albumin	X		X	X		
Total protein	X		X	X		
SGPT	X		X	X		
Alkaline phosphatase	X		X	X		
Bilirubin (total and direct)	X		X	X		
GGT	X		X	X		
AST	X		X	X		
Essential Fatty Acid Profile	X		X	X		2 mL red top
Free cholesterol	X		X	X		
Free fatty acids	X		X	X		
Lipid Panel	X		X	X		
Hemoglobin	X		X	X		0.6ml purple top
Hematocrit	X		X	X		
RBC	X		X	X		
WBC	X		X	X		
Platelets	X		X	X		1.5ml blue top
PT	X		X	X		
PTT	X		X	X		
INR	X		X	X		
Fibrinogen	X		X	X		Navy blue Metal free
Selenium					X	
Zinc					X	
Aluminum					X	
Copper					X	
Iron					X	lithium heparin
Carnitine					X	
Vitamins A,D,E					X	Call lab control
Retinol binding protein (check when getting Vit A)					X	3 ml red top

*More often as necessitated by clinical course; may be reduced in patients who are stable (i.e., home patients) and whose biochemical markers have improved.
